## SUMMARY OF TRIAL

SUMMARY INFORMATION TYPE	SUMMARY DETAILS
ACRONYM	PROUD
Long Title of Trial	Pre-exposure Option for reducing HIV in the UK: an open-label randomisation to immediate or deferred daily Truvada for HIV negative gay men.
Version	1.3
Date	14 October 2014
ISRCTN #	ISRCTN94465371
NCT#	NCT02065986
EudraCT #	2012-002373-56
Study Design	A multi-centre, open label randomised design to immediate or deferred inclusion of pre-exposure prophylaxis as part of the package of HIV risk reduction interventions.
Type of Participants to be Studied	HIV negative men who have unprotected anal intercourse (UAI) with men
Setting	Genito-urinary medicine (GUM) clinics in the UK
Interventions to be Compared	All participants will be offered a risk reduction package that includes regular HIV testing, diagnosis and treatment of sexually transmitted infections (STI), support to reduce and eliminate high risk behaviour including free condoms, and other biomedical interventions such as post-exposure prophylaxis where relevant. With or Without the inclusion of daily oral Truvada.
Study Question	In order to determine whether the immediate inclusion of anti-retroviral pre-exposure prophylaxis (PrEP) as part of the HIV risk reduction package for men who have sex with men who are at risk of acquiring HIV is clinically effective and cost-effective, a large trial would need to be conducted.  The purpose of the pilot is to determine the feasibility of conducting such a trial in the UK.
Main Outcome Measures	Time to accrual of 500 participants Retention at month 12 and 24
Other Outcome Measures	HIV infection between randomisation and month 12 .  Safety: 
 
• Serious Adverse Reactions attributable to Truvada
 
• Adverse events that lead to interruption or cessation of Truvada
 
• Renal function estimated using serum creatinine at 12m
 
• Frequency of viral resistance in men who acquire HIV
 

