### 5.2.3 DOSE MODIFICATIONS AND INTERRUPTIONS

Truvada must be interrupted if a participant suffers a serious adverse event that could be a drug reaction, or if their renal function is confirmed to be abnormal with no clinical explanation, pending further investigation or specialist referral. Renal function will be assessed using either serum creatinine (in the absence of protein supplements) to estimate glomerular filtration rate, or urinary protein to creatinine ratio according to clinic practice.

Truvada can be reintroduced at the discretion of the clinician, following a discussion with the participant, and the dose can be modified to alternate days or 4 days a week. Should the event recur, and Truvada is the likely cause, drug must be discontinued.

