### 6.4 PROCEDURES FOR ASSESSING SAFETY

Participants will be asked one month after starting Truvada and quarterly whether they have had any admissions to hospital, or suffered any significant illnesses that stopped them undertaking their usual daily activities and required medical intervention. A clinical member of the team will determine whether or not an illness that interfered with usual daily activity meets the definitions for Serious Adverse Event (SAE) provided in [Table 7.1: Definitions](#). SAEs should be reported to MRC CTU within 24 hours of the investigator becoming aware of this. Participants will also be asked whether they have had any side-effects sufficient to interrupt or stop their Truvada.

Glomerular filtration rate will be estimated at baseline, and annually. Urinalysis for protein will be assessed at these and interim visits and the presence of 1+ or greater protein that cannot otherwise explained will trigger an additional investigation according to routine clinic practice for patients taking Truvada (either a further creatinine measurement to estimate glomerular filtration rate, or urinary protein:creatinine ratio). In the event that that estimated glomerular filtration rate (eGFR) is less than 50mL/min, or the ratio of protein: creatinine (UPC) greater than 20, the participant will be recalled, their medical history, other medication, dietary supplements and pill taking reviewed, and a repeat test performed in the absence of any protein supplements. If the eGFR is confirmed to be < 50 mL/min or the UPC > 20, then Truvada may need to be interrupted or modified to 4 or less tablets a week pending further investigation and/or referral for specialist opinion. In the event that this leads to discontinuation of Truvada, this meets the definition of 'another important medical condition' as described in [Table 7.1: Definitions](#), and should be reported to MRC CTU within 24 hours of the investigator becoming aware of the event.

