#### 9.2.2 OTHER OUTCOME MEASURES

- HIV infections acquired between trial entry and 12 months, and between 12 and 24 months
- Safety
  - Serious Adverse Reactions attributable to Truvada
  - Any adverse event leading to interruption or discontinuation of Truvada
  - Renal function estimated using serum creatinine at 12 months
  - Presence of viral resistance mutations likely to have been selected by Truvada (K65R, M184V) in participants who acquire HIV infection.
- Adherence:
  - Proportion of doses taken estimated from self-report
  - Proportion of days covered according to dispensing records for the daily schedule
  - Presence of drug as expected in a subset of selected participants
- Risk Compensation:
  - Number of sexual partners with whom had UAI, UIAI and URAI (unprotected defined as without a condom) between trial entry and month 12 and month 12 to month 24
  - Number of acts of AI, protected and unprotected by a condom, between trial entry and month 12 and month 12 to 24
  - Proportion of acts of AI protected by either condom, PrEP or both between trial entry and month 12 and month 12 to 24
  - Sexually transmitted infection (STIs) acquired between trial entry and month 12
  - Sexually transmitted infection (STIs) acquired between month 12 and month 24
- Other:
  - Facilitators and barriers to adherence to a personal risk reduction plan in a subset of selected participants

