### **At the request of the Trial Steering Committee:**

The protocol has been amended to accommodate and implement the Trial Steering Committee recommendations of 9th October 2014, namely that daily oral Truvada be offered to all participants in the PROUD pilot study as soon as possible and continued through to the end of the study. The protocol has also been updated to reflect the constitution of the IDMC.

A new section has been added to the introduction explaining the rationale for the change (Section 1.4). Sections 1.2.4, 5.2, 5.4, 6.6, 7.1.3 have been changed to reflect the earlier offer of PrEP to those in the deferred group from October 2014 onwards and the continued provision of PrEP beyond month 24 while the study is ongoing. Section 9.4 and 14.3 update the independent study monitoring arrangements

At the request of investigators and participants:

Section 5.2.3 has been amended to allow for dose modification when participants who have impaired renal function due to other causes wish and need to continue on Truvada. The modifications allowed are in line with the SMPC that supports the use of Truvada as treatment.

Section 6 has been modified to allow participants to provide the necessary information for safety and behaviour monitoring outside the study clinic times as it has proved easier for participants to attend evening and weekend clinics to have their routine HIV and STI screening and the results are readily available to study staff who can check these before prescribing.

The diaries and questionnaires have proved unpopular with participants and completion has been very low. The online participant database will continue to be available but we will ask participants to complete the monthly questionnaires in clinic during study visits or when they collect drug (Section 6.2.2 and 6.2.3).

Although the lack of daily and monthly behaviour data is disappointing, the annual data are available for analysis and the rate of STIs has been higher than anticipated and these provide an objective marker of risk behaviour. National guidelines have changed since the protocol was implemented and quarterly screens are recommended for MSM having condomless anal intercourse with partners of unknown or HIV negative status. Therefore the schedule has changed to reflect quarterly screens and the inclusion of hepatitis C, regardless of risk, at exit (Section 6.2.3, 6.2.4 is no longer needed, 6.2.5).

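### Protocol 6.4 allows dose reduction for confirmed renal abnormality without limiting it to explained cases, whereas 5.2.3 requires interruption when there is no clinical explanation

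*Protocol*

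**What the plan says.** Two current sections of the protocol tell a clinic what to do with Truvada when renal function is confirmed to be abnormal.

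Section 5.2.3 (Dose modifications and interruptions) makes interruption compulsory. For the renal trigger, the rule applies when the participant's function "is confirmed to be abnormal with no clinical explanation, pending further investigation or specialist referral". Its next paragraph deals with restarting: "Truvada can be reintroduced at the discretion of the clinician, following a discussion with the participant, and the dose can be modified to alternate days". The other reduced schedule it names is 4 days a week. The section gives no numerical definition of abnormal.

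Section 6.4 (Procedures for assessing safety) supplies the definition: eGFR below 50 mL/min, or UPC above 20. A participant who crosses either threshold is recalled, possible causes are reviewed and the test is repeated. If the result is confirmed, "then Truvada may need to be interrupted or modified to 4 or less tablets a week pending further investigation". Specialist referral is named there too.

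Section 7.1.3 directs the reader to 6.4 for the renal checks. Section 6.4 contains no reference to 5.2.3.

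**The concern.** Both sections speak about the same moment: the abnormality is confirmed and its cause is still being looked into. They differ in three ways.

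- **Force.** Section 5.2.3 uses a compulsory verb and 6.4 a permissive one.
- **Options.** Section 5.2.3 gives one action, interruption. Section 6.4 gives two, interruption or a lower dose.
- **Condition.** Section 5.2.3 turns on whether there is a clinical explanation. Section 6.4 drops that distinction at the point where it names the action.

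What is at stake is participant safety. A clinic that follows 6.4 to the letter could leave a participant with confirmed, unexplained renal impairment on a reduced dose of the drug that may be causing it. That would breach 5.2.3 without the clinic knowing. Clinics could also handle the same laboratory result differently, depending on which section they had open.

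**Working it through.** There is no figure in the plan to reproduce. The check is a comparison of the two rules, case by case, with investigation still pending.

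| Confirmed eGFR < 50 mL/min or UPC > 20 | Section 5.2.3 | Section 6.4 |
|---|---|---|
| No clinical explanation | Interrupt (mandatory); reduced dose only with reintroduction | Interrupt or reduce (permissive) |
| Clinical explanation found | No renal instruction | Interrupt or reduce (permissive) |

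1. **Second row.** There is no conflict. Section 5.2.3 is silent, and the options in 6.4 have a sensible use.
2. **First row.** The rules differ. Dose reduction alone satisfies 6.4 as written and breaches 5.2.3. Interruption satisfies both.
3. **Do unexplained cases reach the sentence in 6.4?** Yes. In 6.4 the dipstick route to renal testing starts from proteinuria that has no other explanation. The review at recall will explain some of these cases; the rest arrive at the same permissive sentence.
4. **Would a clinic be led to 5.2.3?** Not by this route. The thresholds are only in 6.4, 7.1.3 points to 6.4, and 6.4 does not point on. The note under Table 7.2 does refer to 5.2.3, but only when drug is interrupted for a related serious adverse event.
5. **Intent.** The version 1.3 entry in section 16 says that 5.2.3 was "amended to allow for dose modification when participants who have impaired renal function due to other causes wish and need to continue on Truvada". This is cited for purpose only, since a change log is not a current rule. It suggests that dose modification was meant for explained impairment, a limit that 6.4 does not carry.

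**Rough scale.** The protocol does not say how many participants cross the thresholds. The nearest figure is in section 1.2.1: 7 of 4,500 trial participants had to stop Truvada for toxicity. Applied to the 545 enrolled, 545 × 7 / 4,500 = 0.85, or about one participant. This is illustrative only. It counts stopping for any toxicity, not confirmed eGFR below 50 or UPC above 20, and threshold crossings could be more or less frequent.

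**The case against.** The strongest reply is that the sections fit together. Section 5.2.3 governs a subset, the unexplained cases. Section 6.4 covers every confirmed result, and permissive wording is natural for a mixed group. The review at recall is the step that separates explained from unexplained cases, the amendment rationale points the same way, and sites must have experience of prescribing Truvada. A clinic that interrupts all unexplained cases complies with both sections, and nowhere does 6.4 say outright that such a case may stay on drug.

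Most of this stands. The reconciled reading is plausible and probably intended. What remains is that 6.4 does not state it. A mandatory safety rule should not depend on the reader finding another section and inferring how the two combine.

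A reader might go further and infer that the safety outcomes are defective. Section 9.2.2 counts "Any adverse event leading to interruption or discontinuation of Truvada", and the trial summary has the matching "Adverse events that lead to interruption or cessation of Truvada", so a participant who is only dose-reduced would not be counted. The protocol does not support making that a finding:

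- Under 5.2.3 an unexplained case is interrupted and therefore counted. It is missed only after a breach of 5.2.3, and only if the drug is never later interrupted or stopped.
- Even then, other routes remain: serious adverse reactions, renal events that the investigator considers important (7.1.2), and the outcome "Renal function estimated using serum creatinine at 12 months". They are partial, but each narrows the gap.
- Counting interruption and discontinuation but not dose change is a design choice, applied consistently in the summary, 7.1.2 and 9.2.2.
- Adding dose change to the side-effect questions at visits would not be what detects an event found by the laboratory.

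**Conclusion.** The concern holds as a drafting conflict in a safety rule. For confirmed, unexplained renal abnormality, 6.4 permits an action that 5.2.3 rules out at that stage, and clinics are directed to 6.4. Severity is minor. Few participants are likely to be affected, although the protocol gives no count, and accrual, retention and the HIV comparison are unchanged.

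The conclusion rests on the protocol text alone. The Working Instructions and case record form are not shown. If they already tell clinics to interrupt unexplained cases, the practical risk is smaller still, but the two sections would still need aligning.

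**What to change.** Replace the action sentence in 6.4 with wording to this effect: *If an eGFR below 50 mL/min or a UPC above 20 is confirmed and has no clinical explanation, Truvada must be interrupted until the cause has been investigated or a specialist consulted (see 5.2.3). Reduced dosing, 4 or fewer tablets a week, is allowed only where the impairment is explained, or on reintroduction under 5.2.3.*

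This point needs no change to 9.2.2, the visit questions or 7.1.2.

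The cost is one amended sentence and a note to sites. The downside is that unexplained cases go without PrEP while they are investigated, but 5.2.3 already requires that. The protection given up relative to a reduced dose is also uncertain on the protocol's own counselling. Section 6.2.1.C warns that risk may not be lowered when 3 or more tablets are missed in the week before unprotected anal intercourse, and 4 tablets a week means missing 7 − 4 = 3.

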## 6.5 OTHER ASSESSMENTS

### 6.5.1 SELF-REPORTED BEHAVIOUR

Self-reported sexual and adherence behaviours will be collected in the daily diary and short and long questionnaires.

The **diary** will be a simple record for noting acts of anal intercourse, whether or not a condom was used throughout, and whether or not a pill was taken each day. The facility to enter this information directly into a database held at MRC CTU will be available for participants that have access to the web, and wish to do this. Data will be identifiable to CTU staff by trial number and date of birth only. Participants that record the diary manually will be asked to post these to MRC CTU or to bring them to their next clinic visit.

Participants will be asked to summarise their sexual and adherence behaviours in the **short (last 30 days) questionnaire** when they attend the study visit or collect drug, and to place these in a sealed envelope for forwarding on to MRC CTU. For participants that are using the participant database, the questionnaires can be completed each month online at home or in clinic..

A **long (last 90 days) questionnaire** that includes lifestyle and well-being questions as well as sexual behaviour will be completed during the clinic visits at baseline, when starting Truvada if earlier than month 12, and at annual visits in private.

**In depth interviews** (one to one discussions) will be conducted in a subset of participants (approximately 50 in the first instance) in clinics with access to staff trained in the technique who are independent of the clinic team. Selection will be directed by MRC CTU together with [name] having reviewed the quantitative data collated from self-report and dispensing returns together with biological data such as drug levels (if available) and STIs. Participants will be selected on the basis that they are representative of various combinations of high/low risk and adherence behaviours. An individual trained in IDI techniques will be provided with a summary of the group data and the pattern of behaviour that the participant being interviewed has followed, although not the specific quantitative detail. They will interview men about sexual and adherence behaviours and PrEP acceptability using the one to one discussion guide (see **Appendix VI**). The one to one discussion will be explained to the participants using the Supplementary Participant Information Sheet (Appendix VII). Written informed consent will be collected prior to participation using the Supplementary Informed Consent Form (Appendix VIII). One to one discussions may be facilitated in person, over the phone or via virtual networks (such as secure web based discussion forums).

### 6.5.2 SEXUAL BEHAVIOUR

The number of partners (any and new) with whom the participant had anal sex in the last 30 (short) or 90 (long) days, as well as more specific questions about the most recent episode(s) of anal intercourse will be collected in the questionnaires.

The number of acts of anal intercourse, and whether or not a condom was used will be recorded in the diary.

Markers of unprotected intercourse such as urethral or rectal gonorrhoea, urethral or rectal chlamydia, early syphilis will be collected every 3 months, and hepatitis C when indicated and at exit.

### 6.5.3 ADHERENCE BEHAVIOUR

Doses taken and missed in relation to unprotected anal intercourse will be provided by the diary.

Participants' perception of their adherence and missed doses in the weeks before and after the last anal sex act without a condom will be recorded in the short questionnaire.

Dispensed drug and unused drug will be recorded on the case record form.

Plasma and/or peripheral blood mononuclear cells will be collected from a sub-set of participants on the IMMEDIATE arm (up to 50 participants). Further samples at additional time points in a larger number of participants may be recommended by the Trial Steering Committee (TSC).

Approximately 100 participants at clinics with this resource will be invited to use a Medication Event Monitoring System (MEMS) cap to record the date and time when they open their pill bottles during the study.

### 6.5.4 IN THE EVENT OF SEROCONVERSION

In the event of a seroconversion, information about all sex acts since the previous negative result, number of new partners, characteristics of partners, and adherence to condoms will be collected as is routine practice. Information regarding adherence to Truvada will also be elicited, if applicable. A sample for analysis of drug levels may be collected.

Participants can continue, should they wish to, to complete the short and long questionnaires and have the STI screens, although these can be collected at their routine HIV clinic visits if more convenient.

In accordance with national guidelines for newly diagnosed individuals, a genotypic drug resistance test should be performed to identify mutations which may have been transmitted from the infecting partner or acquired as a result of exposure to Truvada. This test should be performed on the earliest possible sample after seroconversion and a copy of the result sent to MRC CTU for data entry.

### 6.5.5 ACCEPTABILITY

Men's attitudes regarding the acceptability of the study and PrEP will be collected in the **acceptability questionnaires** at or after the 12 month follow-up visits. After reviewing the quantitative data, a guide on acceptability will be developed for group discussions.

**Group discussions** will be conducted with a subset of participants who have experienced PrEP (approximately 10 group discussions with approximately 8 participants per group by staff trained in

the technique who are independent of the clinic team). Some participants will be purposefully selected for participation in group discussions and others will be invited on an ad hoc basis. Selection will be directed by MRC CTU together with [name] having reviewed the quantitative data collated from self-reported acceptability and adherence questionnaires. The group discussion will be explained to participants using the Supplementary Participant Information Sheet (**SPIS Appendix VII**). Written informed consent will be collected prior to participation using the Supplementary Informed Consent Form (**Appendix VIII**). Group discussions may be facilitated in person or via virtual networks such as secure web based discussion forums.

The acceptability questions focusing on PrEP will be informed by the findings of the group discussions and may result in modifications to the questionnaires.

**Field notes** will be collected about study acceptability during the course of the study by individuals trained in ethnographic participant observation techniques, as described by this group previously. Typically, these will note conversations observed or initiated by the recorder with and between participants, non-participants, clinic staff and community workers. The notes will be anonymous and recorded using the field notes template (**Appendix IX**).

## 6.6 EARLY STOPPING OF FOLLOW-UP

If a participant chooses to discontinue their trial treatment, they should be encouraged to continue in follow-up; if they do not wish to remain on trial follow-up, every effort will be made to establish an acceptable means to ascertain their HIV status at annual and final visit timepoints; however, their final decision must be respected and the participant will be withdrawn from the trial completely should this be their wish, and the appropriate case record form completed.

Participants may change their minds about stopping trial follow-up at any time and re-consent to participation in the trial.

Participants who stop trial follow-up early will not be replaced.

